6.3 Lifestyle Restrictions

6.3.1 Meals and Dietary Restrictions

For participants in Arms A (and Arm B participants enrolled prior to Revised Protocol 01), cabozantinib should not be taken with grapefruit/grapefruit juice or Seville oranges.

For participants in Arm C, sunitinib should not be taken with grapefruit/grapefruit juice.

6.4 Screen Failures

Screen failures are defined as participants who consent to participate in the clinical study but are not subsequently randomized. A minimal set of screen failure information is required to ensure transparent reporting of screen failure participants, to meet the Consolidated Standards of Reporting Trials (CONSORT) publishing requirements, and to respond to queries from regulatory authorities. Minimal information includes date of consent, demography, screen failure details, eligibility criteria, and any serious AEs.

6.4.1 Retesting During Screening or Lead-In Period

Participant Re-enrollment: This study permits the re-enrollment of a participant that has discontinued the study as a pre-treatment failure (ie, participant has not been randomized / has not been treated). If re-enrolled, the participant must be re-consented.

Retesting of laboratory parameters and/or other assessments within any single Screening or Lead-in period will be permitted (in addition to any parameters that require a confirmatory value).

The most current result prior to randomization is the value by which study inclusion will be assessed, as it represents the participant's most current, clinical state.

Laboratory parameters and/or assessments that are included in [Table 2-1 Screening Procedural Outline](#) may be repeated in an effort to find all possible well-qualified participants. Consultation with the BMS Medical Monitor may be needed to identify whether repeat testing of any particular parameter is clinically relevant.

7 TREATMENT

Study treatment is defined as any investigational treatment(s), marketed product(s), placebo or medical device intended to be administered to a study participant according to the study randomization or treatment allocation.

Study treatment includes both Investigational [Medicinal] Product (IP/IMP) and Non-investigational [Medicinal] Product (Non-IP/Non-IMP) and can consist of the following:

An investigational product, also known as investigational medicinal product in some regions, is defined a pharmaceutical form of an active substance or placebo being tested or used as a reference in a clinical study, including products already with a marketing authorization but used or assembled (formulated or packaged) differently than the authorized form, or used for an unauthorized indication, or when used to gain further information about the authorized form.

Other medications used as support or escape medication for preventative, diagnostic, or therapeutic reasons, as components of the standard of care for a given diagnosis, may be considered as non-investigational products.

Table 7-1: Study treatments for CA2099ER

Product Description / Class and Dosage Form	Potency	IP/ Non-IMP	Blinded or Open Label	Packaging / Appearance	Storage Conditions (per label)
BMS-936558-01 (Nivolumab) Solution for Injection*	100 mg (10 mg/mL)	IP	Open Label	Vial (multiple vials per carton)	Store at 2° - 8 °C. Protect from light and freezing
Ipilimumab Solution for Injection (see Note)	200 mg (5mg/mL)	IP	Open Label	Vial (multiple vials per carton)	Store at 2° - 8 °C. Protect from light and freezing
Cabozantinib Tablet	20 mg	IP	Open Label	Tablets in a bottle	Refer to storage conditions on container label
Sunitinib Malate Capsule**	12.5 mg	IP	Open Label	Capsules in various packaging configurations	Refer to storage conditions on container label/package insert

*May be labeled as “BMS-936558-01” or “Nivolumab”

** Sunitinib may be obtained by the investigational sites in certain countries as local commercial product (which may be available as a different potency/package size than listed above) if local regulations allow and agreed to by BMS.

Note: Implementation of CA2099ER Global Revised Protocol 01 stops further randomization into Arm B. Participants previously randomized to Arm B continue with Arm B treatment and continue with Arm B clinically planned events, per protocol

Premedications or medications used to treat infusion-related reactions should be sourced by the investigative sites if available and permitted by local regulations. Solutions used as diluent (ie, 0.9% Sodium Chloride Injection or 5% Dextrose Injection) should also be sourced by investigative sites if available and permitted by local regulations.

7.1 Treatments Administered

The selection and timing of dose for each participant is presented in Table 7.1-1 and the dosing scheduled by cycle is presented in Table 7.1-2.

Table 7.1-1: Selection and Timing of Dose

Arm	Study Treatment	Dosage level(s) and Formulation	Frequency of Administration	Route of Administration
A (Doublet)	Nivolumab	240 mg IV	Every 2 weeks	IV
	Cabozantinib	40 mg (20 mg tablets)	Once daily (QD)	PO
B (Triplet) See Note	Nivolumab	3 mg/kg IV for 4 doses then 240 mg IV	Every 3 weeks (Q3W) for 4 doses then every 2 weeks (Q2W)	IV
	Ipilimumab	1 mg/kg IV for 4 doses	Every 3 weeks (Q3W) for 4 doses	IV
	Cabozantinib	40 mg (20 mg tablets)	Once daily (QD)	PO
C	Sunitinib	50 mg (12.5 mg capsules)	A 6 week cycle, consisting of once daily (QD) regimen for 4 weeks followed by no treatment for 2 weeks.	PO

Abbreviations: IV=intravenous; PO= by mouth.

Note: Implementation of CA2099ER Global Revised Protocol 01 stops further randomization into Arm B. Participants previously randomized to Arm B continue with Arm B treatment and continue with Arm B clinically planned events, per protocol

Table 7.1-2: Dosing Schedule for CA2099ER

Arm	Cycle 1	Cycle 2	Cycle 3	Cycle 4	Cycle 5 and subsequent cycles
Arm A Nivolumab + Cabozantinib (each cycle = 2 weeks)	Nivolumab 240 mg IV on Day 1 + Cabozantinib 40 mg PO QD	Nivolumab 240 mg IV on Day 1 + Cabozantinib 40 mg PO QD	Nivolumab 240 mg IV on Day 1 + Cabozantinib 40 mg PO QD	Nivolumab 240 mg IV on Day 1 + Cabozantinib 40 mg PO QD	Nivolumab 240 mg IV on Day 1 + Cabozantinib 40 mg PO QD
Arm B Nivolumab + Ipilimumab + Cabozantinib (see Note) (Cycle 1 to 4 = 3 weeks, Cycle 5 and subsequent cycles = 2 weeks)	Nivolumab 3 mg/kg IV on Day 1 + Ipilimumab 1 mg/kg IV on Day 1 + Cabozantinib 40 mg PO QD	Nivolumab 3 mg/kg IV on Day 1 + Ipilimumab 1 mg/kg IV on Day 1 + Cabozantinib 40 mg PO QD	Nivolumab 3 mg/kg IV on Day 1 + Ipilimumab 1 mg/kg IV on Day 1 + Cabozantinib 40 mg PO QD	Nivolumab 3 mg/kg IV on Day 1 + Ipilimumab 1 mg/kg IV on Day 1 + Cabozantinib 40 mg PO QD	Nivolumab 240 mg IV on Day 1 + Cabozantinib 40 mg PO QD

Table 7.1-2: Dosing Schedule for CA2099ER

Arm	Cycle 1	Cycle 2	Cycle 3	Cycle 4	Cycle 5 and subsequent cycles
Arm C Sunitinib (each cycle = 6 weeks, treatment for 4 weeks then 2 weeks off each cycle)	Sunitinib 50 mg PO QD x 4 weeks	Sunitinib 50 mg PO QD x 4 weeks	Sunitinib 50 mg PO QD x 4 weeks	Sunitinib 50 mg PO QD x 4 weeks	Sunitinib 50 mg PO QD x 4 weeks

Abbreviations: IV=intravenous; PO= by mouth; QD= once daily

Note: Implementation of CA2099ER Global Revised Protocol 01 stops further randomization into Arm B. Participants previously randomized to Arm B continue with Arm B treatment and continue with Arm B clinically planned events, per protocol

Participants should begin study treatment within 3 days (72 hours) of randomization.

For **Arm A**, participants should receive nivolumab at a dose of 240 mg as an approximately 30 minute infusion on Day 1 of each treatment cycle until progression, unacceptable toxicity, withdrawal of consent, completion of 24 months of treatment (from the first dose on Cycle 1), or the end of the study, whichever occurs first. The first cabozantinib dose should be given in the evening on Day 1, Cycle 1 (after the Cycle 1 nivolumab dose).

For **Arm B (Note: only applicable to participants who randomized to Arm B prior to Revised Protocol 01)**, when nivolumab and ipilimumab are to be administered on the same day, nivolumab is to be administered first. Nivolumab infusion (approximately 30 minutes) must be promptly followed by a flush of diluent to clear the line of nivolumab before starting the ipilimumab infusion. The second infusion will always be the ipilimumab study drug (approximately 30 minutes infusion) and will start after the infusion line has been flushed, filters changed and participant has been observed to ensure no infusion reaction has occurred. The time in between infusions is expected to be at least 30 minutes (from the end of the nivolumab infusion to the start of the ipilimumab infusion). The first cabozantinib dose should be given in the evening on Day 1, Cycle 1 (after the Cycle 1 nivolumab and ipilimumab doses).

Starting with Cycle 5 in Arm B, participants should receive nivolumab at a dose of 240 mg as a 30 minute infusion on Day 1 of each treatment cycle until progression, unacceptable toxicity, withdrawal of consent, completion of 24 months of treatment (from the first dose on Cycle 1), or the end of the study, whichever occurs first.

Dosing calculations for nivolumab and ipilimumab should be based on the body weight assessed at baseline. It is not necessary to re-calculate subsequent doses if the participant weight is within 10% of the weight used to calculate the previous dose. All doses should be rounded up or to the nearest milligram per institutional standard.

There will be no dose escalations or reductions of nivolumab or ipilimumab allowed. Participants may be dosed with nivolumab no less than 12 days from the previous dose during q2w cycles.

Participants may be dosed with nivolumab and ipilimumab no less than 19 days from the previous dose during q3w cycles (ie, Cycles 1-4 in Arm B). Participants in Arm B may be dosed with the first nivolumab maintenance dose (Cycle 5) no less than 19 days from the previous nivolumab and ipilimumab doses. Premedications are not recommended for the first dose of nivolumab or ipilimumab.

Participants should be carefully monitored for infusion reactions during nivolumab and/or ipilimumab administration. If an acute infusion reaction is noted, participants should be managed according to [Section 7.4.4](#).

Doses of nivolumab and/or ipilimumab may be interrupted, delayed, or discontinued depending on how well the participant tolerates the treatment. Dosing visits are not skipped, only delayed. The only exception is Cycle 4 in Arm B, which may be skipped (omitted) only for the reasons specified in [Section 7.4.3.1](#) and [Section 8.1.1](#) below.

7.1.1 Nivolumab

Nivolumab Injection, 100 mg/10 mL (10 mg/mL) is to be administered as an IV infusion through a 0.2-micron to 1.2-micron pore size, low-protein binding in-line filter at the protocol-specified doses. It is not to be administered as an IV push or bolus injection. Please refer to the Investigational Brochure/pharmacy manual for further details regarding storage, preparation and administration. Care must be taken to assure sterility of the prepared solution as the product does not contain any antimicrobial preservative or bacteriostatic agent.

7.1.2 Ipilimumab (Participants Randomized to Arm B Prior to Revised Protocol 01)

For details regarding ipilimumab storage, preparation, and administration, please refer to the instructions in the ipilimumab IB and/or pharmacy manual.

Separate infusion bags and filters should be used when administering nivolumab and ipilimumab on the same day.

Care must be taken to assure sterility of the prepared solutions, since the drug product does not contain any antimicrobial preservatives or bacteriostatic agents.

7.1.3 Cabozantinib

Cabozantinib is taken orally on an empty stomach, preferably at bed time. Participants should fast (with the exception of water) for at least 2 hours before until 1 hour after each dose of cabozantinib. Cabozantinib tablets should not be crushed or chewed. Cabozantinib should not be taken with grapefruit/grapefruit juice or Seville oranges. Missed doses of cabozantinib should not be taken within 12 hours of the next dose.

Dispense cabozantinib tablets in their original containers.

7.1.4 Sunitinib

Sunitinib is taken orally without regard to meals. Participants are to avoid grapefruit/grapefruit juice while on treatment with sunitinib.

7.2 Method of Treatment Assignment

All participants will be centrally randomized using an Interactive Response Technology (IRT). Before the study is initiated, each user will receive log in information and directions on how to access the IRT. Specific instructions for using IRT will be provided to the investigational site in a separate document.

The investigator or designee will register the participant for enrollment by following the enrollment procedures established by BMS.

Once enrolled in IRT, enrolled participants that have met all eligibility criteria, including determination of PD-L1 expression in the tumor sample submitted to and evaluated by the central laboratory, will be ready to be randomized through the IRT prior to the start of study treatment administration for each participant. The site will record the treatment assignment on the applicable case report form, if required.

Study treatment will be dispensed at the study visits as listed in Schedule of Activities ([Section 2](#)).

7.3 Blinding

Not applicable as this is an open-label study; however, the specific treatment to be taken by a participant will be assigned using an Interactive Response Technology (IRT).

Treatment assignments will be released to the bioanalytical laboratory in order to minimize unnecessary analysis of samples.

BICR will remain blinded to treatment assignment.

7.4 Dosage Modification

CA2099ER Global Revised Protocol 01

Implementation of CA2099ER Global Revised Protocol 01 stops further randomization into Arm B. Participants previously randomized to Arm B continue with Arm B treatment and continue with Arm B clinical planned events, per protocol.

In Arm A and Arm B, the assessment of causality for any AE should be performed independently for each study drug in the combination regimen.

In the doublet treatment arm (Arm A), cabozantinib and nivolumab will be administered at Cycle 1. After Cycle 1, modifications in cabozantinib dosing (delay, reduction/escalation, and discontinuation) may occur as outlined in [Section 7.4.1](#), [Section 7.4.2](#), and [Section 8](#). After Cycle 1, nivolumab may be modified as outlined in [Section 7.4.1](#), [Section 7.4.2](#), and [Section 8](#).

In the triplet treatment arm (Arm B), cabozantinib, nivolumab, and ipilimumab will be administered at Cycle 1. After Cycle 1, modifications in cabozantinib dosing (delay, reduction/escalation, and discontinuation) may occur as outlined in [Section 7.4.1](#), [Section 7.4.2](#), and [Section 8](#). After Cycle 1, nivolumab or ipilimumab may be modified as outlined in [Section 7.4.1](#), [Section 7.4.2](#), and [Section 8](#).

In Arm C, sunitinib will be administered at Cycle 1. After Cycle 1, modifications in sunitinib dosing (delay, reduction/escalation, and discontinuation) may occur as outlined in Section 7.4.1, Section 7.4.2, and Section 8.

7.4.1 Dose Delay Criteria

Dose delay criteria for management of adverse events during nivolumab, ipilimumab, cabozantinib, or sunitinib treatment are outlined in this section.

Dosing of nivolumab (in Arm A) or nivolumab and ipilimumab (in Arm B) may be delayed without delay of cabozantinib dosing if toxicity is felt to be related to only nivolumab (Arm A) or nivolumab and ipilimumab (Arm B) and not related to cabozantinib. Conversely, dosing of cabozantinib may be delayed without delay of nivolumab dosing (in Arm A) or nivolumab and ipilimumab dosing (in Arm B) if toxicity is felt to be related to only cabozantinib and not related to nivolumab (Arm A) or nivolumab and ipilimumab (Arm B). However, if toxicity is considered related to all study drugs or if the investigator is unable to determine which study drug is the cause of the AE, then all study drugs in the combination should be delayed.

Participants who require dose delay should be re-evaluated weekly or more frequently if clinically indicated and resume dosing when re-treatment criteria are met (see Section 7.4.3).

7.4.1.1 Dose Delay Criteria for Nivolumab and Ipilimumab

In Arm A, nivolumab administration should be delayed, and in Arm B, both nivolumab and ipilimumab administration should be delayed, for any of the following:

- Any Grade ≥ 2 non-skin, drug-related AE, with the exception of fatigue
- Grade 2 drug-related creatinine, AST, ALT, and/or total bilirubin abnormalities
- Any Grade 3 skin, drug-related AE
- Any Grade 3 drug-related laboratory abnormality, with the following exceptions:
 - Grade 3 lymphopenia does not require dose delay
 - Grade 3 amylase or lipase abnormalities that are not associated with symptoms or clinical manifestations of pancreatitis do not require a dose delay.
 - Grade ≥ 3 AST, ALT or total bilirubin will require dose discontinuation (see section 8.1.1)
- Any adverse event, laboratory abnormality, or intercurrent illness which, in the judgment of the investigator, warrants delaying the dose of study medication.

During Cycles 1-4 in Arm B, both nivolumab and ipilimumab must be delayed at the same time.

Immuno-oncology agents, such as nivolumab and ipilimumab, are associated with AEs that differ in severity and duration than AEs caused by other therapeutic classes. Early recognition and management of AEs associated with immuno-oncology agents may mitigate severe toxicity. Management Algorithms have been developed to assist investigators in assessing and managing the following groups of AEs:

- Gastrointestinal
- Renal
- Pulmonary

- Hepatic
- Endocrinopathy
- Skin
- Neurological

The management algorithms recommended for use in CA2099ER are included in [Appendix 5](#).

7.4.1.2 Dose Delay Criteria for Cabozantinib

Cabozantinib dosing should be delayed for the following:

- Urine protein/creatinine ratio (UPCR) > 2.0 *or* urine dipstick protein \geq 3+ *or* urine protein > 2.0 g / 24 hours. Obtain 24 hour urine protein prior to next dosing visit.
- Grade 3 prolonged QTc interval (ie, QTcF interval > 500 msec on at least 2 out of 3 separate ECGs performed at least 3 minutes apart)
- Any Grade 2 or 3 drug-related venous thrombosis requiring anticoagulation, with the following exception:
 - Any recurrent or worsening venous thromboembolic event after restarting cabozantinib will require discontinuation
- Any other Grade 2 drug-related adverse event or grade 2 drug-related laboratory abnormality (e.g., AST, ALT, total bilirubin) that persists for more than 1 week or worsens despite supportive care management, with the following exception:
 - Any Grade 2 drug-related hemorrhage requires dose delay
 - Grade \geq 2 arterial thromboembolic events, including cerebrovascular ischemia, cardiac ischemia/infarction, peripheral or visceral arterial ischemia, require discontinuation
- Sustained Grade 3 drug-related hypertension (systolic BP \geq 160 mm Hg or diastolic BP \geq 100 mm Hg). NOTE: Stopping or reducing the dose of cabozantinib is expected to cause a decrease in BP. The treating physician should monitor the participant for hypotension and adjust the number and dose of antihypertensive medications accordingly.
- Any other Grade 3 drug-related adverse event or laboratory abnormality, with the following exceptions:
 - Grade \geq 3 drug-related hemorrhage requires discontinuation ([Section 8.1.2](#)).
 - Drug-related AST or ALT > 8 x ULN requires discontinuation ([Section 8.1.2](#)).
 - Concurrent AST or ALT > 3 x ULN and total bilirubin > 2 x ULN, consistent with potential drug-induced liver injury (see [Section 9.2.7](#)), requires discontinuation ([Section 8.1.2](#))
 - Grade 3 drug-related amylase or lipase abnormalities that are not associated with symptoms or clinical manifestations of pancreatitis do not require dose delay. In such cases, more frequent monitoring (eg, weekly) of amylase and lipase is recommended. If amylase or lipase worsen to Grade 4 severity or the participant develops symptoms or clinical manifestations of pancreatitis, dosing should be delayed.
- Grade 4 drug-related amylase or lipase abnormalities require dose delay. Participants should be monitored for development of symptoms or clinical manifestations of pancreatitis.
- Grade 4 drug-related electrolyte abnormalities require dose delay. Electrolyte correction with supplementation/appropriate management should be promptly initiated.

- Grade 4 drug-related neutropenia, lymphopenia, leukopenia, anemia, or thrombocytopenia
- Any adverse event, laboratory abnormality, or intercurrent illness which, in the judgment of the investigator, warrants delaying cabozantinib dosing
- For participants scheduled for major surgery, including dental surgery which may impact bone healing, cabozantinib dosing should be delayed at least 28 days prior to scheduled surgery. The treating physician should use clinical judgment with regard to the risks and benefits of the planned surgical procedure if it is not possible to delay cabozantinib dosing for 28 days prior to the procedure. A delay of cabozantinib dosing of 5 to 7 days is recommended for healing for minor surgery.

As a general approach, all AEs related to cabozantinib should be managed with supportive care when possible at the earliest signs of toxicity. Calcium, magnesium, potassium, and phosphorus should be kept above the lower limits of the laboratory normal values. Please refer to the cabozantinib IB, [Appendix 10](#), and [Appendix 11](#) for additional information regarding dose modifications and AE management.²¹

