7.4.1.3 Dose Delay Criteria for Sunitinib

Sunitinib dose delays should be based on instructions in the approved product label and should be considered for any severe or intolerable drug-related adverse events.

Within a cycle, missed doses of sunitinib should be skipped. Participants should never be dosed during the 2-week off period of each 6-week cycle, even if treatment delays occurred earlier in the cycle and therapy is ready to be resumed. If treatment is delayed past the end of the 6-week cycle, the start of the next cycle should be delayed until treatment with sunitinib resumes.

Prior to resuming therapy after a dose delay, refer to [Section 7.4.2](#) for dose reduction recommendations and [Section 8](#) for discontinuation criteria.

For this protocol, sunitinib dosing should be delayed for any of the following:

- Urine protein/creatinine ratio (UPCR) ≥ 2.0 or urine dipstick protein $\geq 3+$ or urine protein ≥ 2.0 g / 24 hours. Obtain 24 hour urine protein prior to next dosing visit.
- Grade 3 prolonged QTc interval (ie, QTcF interval > 500 msec on at least 2 out of 3 separate ECGs performed at least 3 minutes apart)
- Any Grade 2 or 3 drug-related venous thrombosis requiring anticoagulation, with the following exception:
 - Any recurrent or worsening venous thromboembolic event after restarting sunitinib will require discontinuation
- Any other Grade 2 drug-related adverse event that persists or worsens despite supportive care management, with the following exception:
 - Any Grade 2 drug-related hemorrhage requires dose delay
 - Grade ≥ 2 arterial thromboembolic events, including cerebrovascular ischemia, cardiac ischemia/infarction, peripheral or visceral arterial ischemia, require discontinuation
- Grade 3 drug-related hypertension (systolic BP ≥ 160 mm Hg or diastolic BP ≥ 100 mm Hg). NOTE: Stopping or reducing the dose of sunitinib is expected to cause a decrease in BP. The

treating physician should monitor the participant for hypotension and adjust the number and dose of antihypertensive medications accordingly.

- Any other Grade 3 drug-related adverse event or laboratory abnormality, with the following exceptions:
 - Grade \geq 3 drug-related hemorrhage requires discontinuation (Section 8.1.2).
 - Drug-related AST or ALT $>$ 8 x ULN requires discontinuation (Section 8.1.2).

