7.4.2.2 Dose Reduction and Escalation for Cabozantinib

Dose reductions and dose escalations for adverse event management are allowed for cabozantinib (Table 7.4.2-1). Cabozantinib doses will not be re-escalated once reduced, unless a concomitant strong CYP3A4 inducer is started (see below). The only exception is participants who continue on cabozantinib alone after discontinuation of nivolumab alone (Arm A) or discontinuation of both nivolumab and ipilimumab (Arm B) who may re-escalate one dose level if the prior dose reduction was due to a toxicity felt by the investigator to have been mainly related to nivolumab and/or ipilimumab.

After toxicity requiring a dose delay has improved and meets the criteria to resume dosing (Section 7.4.3.2), participants who were receiving cabozantinib 40 mg daily prior to the delay will resume cabozantinib at 20 mg daily. Participants who were receiving cabozantinib 20 mg daily prior to the delay and require another dose delay will resume cabozantinib at 20 mg every other day. If more than 2 dose reductions are necessary (ie, reduction to less than 20 mg every other day), cabozantinib must be permanently discontinued (Section 8.1.2).

Participants who required a dose delay due to Grade 3 hypertension, which improved with antihypertensive medications, or any Grade 2 or 3 drug-related adverse event or asymptomatic laboratory abnormality that improved to Grade ≤ 1 within 7 days with supportive medical care may resume cabozantinib at the same dose or a reduced dose, at the discretion of the investigator.

Participants with asymptomatic Grade 2 drug-related AST, ALT or total bilirubin elevation, or Grade 3 drug-related lipase or amylase abnormalities that are not associated with symptoms or clinical manifestations of pancreatitis may reduce cabozantinib by one dose level, without delaying dosing, at the discretion of the investigator. See also section 7.4.1.2.

In Participants Who Start Taking a Concomitant Strong CYP3A4 Inhibitor: Reduce the daily cabozantinib dose by 20 mg (for example, from 40 mg to 20 mg daily). Resume the dose that was used prior to initiating the CYP3A4 inhibitor 2 to 3 days after discontinuation of the strong inhibitor (see Prescribing Information for cabozantinib).

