7.4.3.2 Criteria to Resume Cabozantinib Treatment

Participants may resume treatment with cabozantinib when the drug-related AE(s) resolve to Grade \leq 1 or baseline value, with the following exceptions:

- Participants may resume dosing in the presence of Grade 2 fatigue
- Participants who delayed dosing due to prolonged QTcF may resume dosing at one reduced dose level once QTcF returns to \leq 500 msec
- Participants who delayed dosing due to UPCr $>$ 2.0 or urine dipstick protein \geq 3+ or urine protein $>$ 2.0 g / 24 may resume dosing at one dose level reduction when UPCr is \leq 2.0 or 24 hour urine protein \leq 2.0 g /24
- Participants who delayed dosing due to Grade 3 hypertension may resume dosing at the same dose or at one dose level reduction, at the discretion of the investigator, when hypertension has improved to Grade \leq 2
- Participants who delayed dosing due to Grade 4 lipase or amylase abnormalities may resume dosing upon resolution to Grade \leq 2
- Participants who delayed dosing due to major surgery should not resume cabozantinib until complete wound healing has taken place. Following cabozantinib resumption, participants should be monitored for wound dehiscence, wound infections, and other signs of impaired wound healing.
- Participants who develop a pulmonary embolism and/or DVT should have study treatment interrupted until therapeutic anticoagulation is established. Treatment with cabozantinib may be resumed in subjects with pulmonary embolism or DVT if it is determined that the event is uncomplicated and that the subject is deriving clinical benefit from cabozantinib treatment and that anticoagulation does not place them at a significant risk that outweighs the benefit of resuming treatment per discretion of the investigator.
- Participants who delayed dosing due to \leq Grade 2 hemorrhage may resume dosing if bleeding is under control (recovered to at least Grade 1 level) and has a low risk of recurrence
- If treatment is delayed $>$ 6 weeks for any reason, the participant must be permanently discontinued from study therapy, except in cases where permission to resume treatment is granted by the BMS Medical Monitor or designee.

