7.4.3.3 Criteria to Resume Sunitinib Treatment

Within a cycle, missed doses of sunitinib should be skipped and not replaced. Participants should never be dosed during the 2-week off period of each 6-week cycle, even if treatment delays occurred earlier in the cycle and therapy is ready to be resumed. If treatment is delayed past the end of the 6-week cycle, the start of the next cycle should be delayed until treatment with sunitinib resumes.

Participants may resume treatment with sunitinib when the drug-related AE(s) resolve to Grade \leq 1 or baseline value, with the following exceptions:

- Participants may resume dosing in the presence of Grade 2 fatigue
- Participants who delayed dosing due to prolonged QTcF may resume dosing at one reduced dose level once QTcF returns to \leq 500 msec
- Participants who delayed dosing due to UPCr \geq 2.0 or urine dipstick protein \geq 3+ may resume dosing at one dose level reduction when 24 hour urine protein $<$ 2.0 g
- Participants who delayed dosing due to Grade 3 hypertension may resume dosing at the same dose or at one dose level reduction, at the discretion of the investigator, when hypertension has improved to Grade \leq 2
- Participants who delayed dosing due to Grade 4 lipase or amylase abnormalities may resume dosing upon resolution to Grade \leq 2
- Participants who develop a pulmonary embolism and/or DVT should have study treatment interrupted until therapeutic anticoagulation is established. Treatment with cabozantinib may be resumed in subjects with pulmonary embolism or DVT if it is determined that the event is uncomplicated and that the subject is deriving clinical benefit from cabozantinib treatment and that anticoagulation does not place them at a significant risk that outweighs the benefit of resuming treatment per discretion of the investigator.
- Participants who delayed dosing due to \leq Grade 2 hemorrhage may resume dosing if bleeding is under control (recovered to at least Grade 1 level) and has a low risk of recurrence
- If treatment is delayed $>$ 6 weeks for any reason, the participant must be permanently discontinued from study therapy, except in cases where permission to resume treatment is granted by the BMS Medical Monitor or designee.

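### The mandatory stop for a repeat venous clot is missing from the PE/DVT resume rules and both discontinuation lists, and the sunitinib resume rule names cabozantinib

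*Protocol*

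**What the plan says.** **The stop.** Sections 7.4.1.2 and 7.4.1.3 of the protocol delay dosing for Grade 2 or 3 drug-related venous thrombosis that needs anticoagulation. Each then carves out one exception. For cabozantinib: "Any recurrent or worsening venous thromboembolic event after restarting cabozantinib will require discontinuation". For sunitinib: "Any recurrent or worsening venous thromboembolic event after restarting sunitinib will require discontinuation".

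**Resuming cabozantinib.** Section 7.4.3.2 has an item specific to these events. It begins "Participants who develop a pulmonary embolism and/or DVT should have study treatment interrupted until therapeutic anticoagulation is established". It then lets cabozantinib restart, at the investigator's discretion, if the event is uncomplicated, the participant is benefiting, and anticoagulation does not add a risk that outweighs the benefit.

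**Resuming sunitinib.** Section 7.4.3.3 opens with the general rule, "Participants may resume treatment with sunitinib when the drug-related AE(s) resolve to Grade" 1 or lower, or to baseline, and then lists exceptions. The PE/DVT exception reads "Treatment with cabozantinib may be resumed in subjects with pulmonary embolism or DVT if it is determined that the event is uncomplicated", with the further condition that "the subject is deriving clinical benefit from cabozantinib treatment".

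**Discontinuation lists.** Section 8.1.2 (cabozantinib) lists arterial thromboembolic events but has no item specific to venous events. Section 8.1.3 (sunitinib) lists venous thrombosis only when it is Grade 4, drug-related and symptomatic.

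**The concern.** A site deciding whether to restart a drug after a clot will look at the resume section and the discontinuation list. For a second or worsening Grade 2-3 event on cabozantinib, the resume item read by itself points to restart at discretion, while the dose-delay section requires permanent discontinuation. The list a site would check before restarting does not settle the matter, because the stop is not in it.

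In Arm C the difficulty is different. Participants there receive only sunitinib, yet the item meant to govern restart after PE or DVT speaks only of cabozantinib. If it is read literally, the arms follow different rules: Arm A may restart once anticoagulation is established, while Arm C must wait for resolution to Grade 1 or lower or baseline. Arm C also faces the 6-week limit on delays, unless the sponsor's medical monitor agrees otherwise.

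**Working it through.** No arithmetic beyond counting applies. The check sets the sections side by side.

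**Step 1. Which rule governs on a full reading.** Section 7.4.1 says "Participants who require dose delay should be re-evaluated weekly or more frequently if clinically indicated and resume dosing when re-treatment criteria are met". Section 7.4.2.2 has the same sequence for cabozantinib: "After toxicity requiring a dose delay has improved and meets the criteria to resume dosing", dosing restarts at a lower level. Resumption therefore follows a delay, and a recurrence is excepted from delay. Section 7.4 also names 7.4.1, alongside 7.4.2 and Section 8, as a source of discontinuation rules. On the better reading the stop governs.

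**Step 2. Whether the resume item respects it.** The item in 7.4.3.2 covers anyone who develops a PE or DVT. It carries its own interruption instruction and restart test, is not tied to a prior delay, does not separate a first event from a repeat, and does not point back to 7.4.1.2. Resume items that exclude a recurrence: 0 of 2 (7.4.3.2 and 7.4.3.3).

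**Step 3. Whether the cabozantinib list repeats the stop.**

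| Stop rule in 7.4.1.2 | Points to 8.1.2 | Listed in 8.1.2 |
|---|---|---|
| Recurrent or worsening venous event | No | No |
| Grade 2 or higher arterial event | No | Yes |
| Grade 3 or higher hemorrhage | Yes | Yes |
| AST or ALT > 8 x ULN | Yes | Yes |
| AST or ALT > 3 x ULN with bilirubin > 2 x ULN | Yes | Yes |
| **Total of 5** | **3** | **4** |

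Only the venous rule has neither.

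**Step 4. The sunitinib list.** Section 8.1.3 covers only Grade 4 symptomatic venous thrombosis, plus a general item for other Grade 4 drug-related events. The recurrence stop is therefore stated in 0 of 2 discontinuation lists. Section 7.4.1.3 tells sites to consult Section 8 for discontinuation criteria before resuming after a delay, and that leads to a list without the stop.

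**Step 5. Drug named in the 7.4.3.3 item.** Cabozantinib: 2 times. Sunitinib: 0 times. The interruption sentence refers to study treatment in general and so applies to Arm C; the restart sentence does not. What remains in the protocol for restarting sunitinib is the general rule at the head of 7.4.3.3.

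**Step 6. Who is exposed.** Drug-related Grade 4 events are caught by 8.1.2 and 8.1.3. For the gaps in Steps 2 to 4, that leaves recurrent or worsening Grade 2-3 events judged uncomplicated, with clinical benefit and acceptable anticoagulation risk. The drug-name error reaches further, because it also touches a first PE or DVT on sunitinib.

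**The case against.** The strongest reply is that the sections do not conflict. The stop is specific and mandatory, the resume item is general and permissive, and the protocol's sequence sends only delayed participants to the resume criteria. That stands as the better reading. The fault is a missing exception and incomplete lists, not a reversal of the rule. Nor do 8.1.2 and 8.1.3 claim to be exhaustive, so their silence is an omission and not a permission to continue.

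A second reply is that other resume items in 7.4.3.2 also leave out their stops: Grade 3 hypertension without persistent hypertension, proteinuria without nephrotic syndrome, Grade 4 lipase or amylase without pancreatitis. This does not carry over. Those stops are all covered in 8.1.2, and the venous one is not. Those items are also worded for participants whose dosing was already delayed, which the PE/DVT item is not.

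Third, the Step 3 count is for cabozantinib only. That is right, and it does not transfer: the pointers in 7.4.1.3 cite 8.1.2 and not 8.1.3. For sunitinib the point rests on the text of 8.1.3 alone.

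Fourth, the intended drug in 7.4.3.3 is plain from the heading, and sunitinib management also defers to the product label, which is not among the documents. Both are fair. Most sites would probably infer the meaning, and the label may add guidance. The protocol text is still wrong as written.

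**Conclusion.** The concern holds, as a minor inconsistency. The mandatory stop is stated for both drugs in the dose-delay sections. It is absent from both PE/DVT resume items and both discontinuation lists, and the sunitinib resume item names the wrong drug at both mentions.

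Confidence is high because each point can be read directly from unredacted text. The minor rating rests on three things: the stop survives a full reading; the exposed group for the recurrence gap is narrow; and the items in 8.1.2 and 8.1.3 that let the investigator stop for substantial clinical risk give further cover. How often such events would occur cannot be judged, since the documents give no rate. There is no consequence for alpha, power or sample size.

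**What to change.** Keep the mandatory stop and make the other sections agree with it:

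- Add a recurrent or worsening venous thromboembolic event after restart to the lists in 8.1.2 and 8.1.3.
- In the PE/DVT items of 7.4.3.2 and 7.4.3.3, except a recurrent or worsening event after restart and state that it requires discontinuation.
- In the 7.4.3.3 item, replace cabozantinib with sunitinib at both places.
- As a clerical correction in the same amendment, change the reference in 7.4.2.3 that sends the reader to 7.4.2.3 itself for dose-delay advice, so that it points to 7.4.1.3.

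The cost is a few lines of protocol wording, with no new procedures, data or analyses.
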